- Symptomatic vertebral stenosis resulting from presumed atheromatous disease.
- Severity of stenosis at least 50% as determined by MRA or CTA or intra-arterial angiography.
- Symptoms of TIA or non-disabling stroke within the last three months.
- Patient able to provide written informed consent, be willing to be randomised to either treatment, and be willing to participate in follow-up.
- If randomised to stenting, this can be performed within two weeks after randomization.

Exclusion Criteria:

- Patients unwilling or unable to give informed consent.
- Patients unwilling to accept randomisation to either treatment arm.
- Vertebral stenosis caused by acute dissection as this has a different natural history and usually spontaneously improves.
- Patients in whom vertebral stenting is felt to be technically not feasible e.g. access problems.
- Previous stenting in the randomised artery.
- Pregnant and lactating women.

RANDOMISATION

Randomisation will be stratified by the site of vertebral stenosis.

Stent Register

A log of stented patients with symptomatic vertebral stenosis not randomised to the trial will be kept at participating centres. This will allow us to determine whether a significant proportion of patients receiving stenting were not entered into the study and had open treatment. This will help assess any overall bias in the study.

Consent

Written informed consent will be obtained from all patients. All patients will be provided with a written information sheet explaining the study.

PATIENT ASSESSMENT SCHEDULE

Patient assessments will take place at the following time points;

- Hospital Visit 1 Baseline Visit
- Hospital Visit 2 At randomisation (if allocated to stenting)
- Hospital Visit 3 at One Month post randomisation
- Telephone Follow-up Call at 6 months
- Hospital Visit 4 at One Year
- Telephone Follow-up Call Yearly from year 2 onward until study end

Follow-up will range from 2 years for the last recruited patients to up to about 8 years for first patients recruited.

At each hospital visit neurological assessment and recording of TIA, stroke and other complications will be performed. Full cardiovascular risk factor assessment will be made.

Patient follow-up post procedure and at one month and one year will be performed by a designated neurologist or stroke physician. All other follow-up will be performed using telephone follow-up.

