For UK patients only, health and social care contacts during the first two years will be collected prospectively using patient diaries. Hospital contacts will also be obtained from patient records. The EQ-5D (www.euroqol.org) will be administered at each follow-up.

To help prevent the loss of participants to follow-up and accurately measure study outcomes, cases in the UK are tracked using the NHS Information Centre Medical Research Information Service. This will include providing relevant information to the Chief Investigator when the following occur during follow up:

- A participant dies
- A participants Primary Care Trust (PCT) changes

Where contact with a subject has been lost and a notification of PCT change has been received, the Chief Investigator will contact the PCT to request details of the participants new General Practitioner (GP). Subsequently the Chief Investigator will then contact the identified GP to request the contact detail of the participant or that his contact details are passed onto the participant.

All end-points or serious adverse events will be reviewed by an independent adjudication committee.

Imaging of the Vertebral Arteries

Prior to randomisation the likely presence of a vertebral stenosis must be demonstrated on imaging. The following imaging modalities are acceptable:

- Magnetic resonance angiography (preferably contrast enhanced)
- Contrast enhanced CT angiography
- Intra-arterial digital subtraction angiography

In the interventional arm digital subtraction angiography will be performed prior to angioplasty/stenting. Stenosis will be measured by a NASCET type method. The residual lumen will be divided by vessel diameter at a point distal to the stenosis where normal vessel calibre has been restored.

Copies of all angiographic will be collected centrally. Information on collateral supply will be collected.

Follow-Up Imaging

Follow-up imaging will be performed in both the interventional and medical arms.

All patients will be followed up with either MRA or CTA at 1 year. Magnetic resonance angiography or CT angiography will be performed to check for vessel patency although it is recognised that in patients with stents these modalities are unlikely to give good quality images of the degree of stenosis.

In all patients with recurrent symptoms (TIA or stroke) repeat brain imaging and vertebral imaging will be performed.

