The investigator must ensure that follow-up of the patient is appropriate to the nature of the event, and that it continues until resolution. He/She must immediately inform the Sponsor of any secondary worsening. Any change in terms of diagnosis, intensity, seriousness, measures taken, causality or outcome regarding an adverse event already reported by following the procedure previously mentioned.

ECONOMIC ANALYSIS (UK patients only)

We will undertake a detailed analysis of the cost and cost-effectiveness of vertebral angioplasty and stenting for symptomatic vertebral stenosis versus best medical treatment. We will estimate cost and cost-effectiveness during the 'within-trial' period (within-trial model) and also over the expected lifetime of the patient (lifetime/long-run model) – we anticipate that over 80% of study participants will still be alive at 5 years. Since we anticipate that the UK will recruit most patients to the trial, costs will be assessed from the perspective of the NHS and personal social services (PSS) in the UK, based on resource use data collected from UK patients only.

Cost components collected during the trial and included in the analysis will consist of the detailed cost of: angioplasty and stenting procedures; best medical treatment; imaging; thrombolysis; length of hospital stay by type of unit/ward (hyperacute stroke unit, acute stroke unit, general ward); outpatient visits by type of unit; physiotherapy, speech therapy, occupational therapy after discharge; primary care contacts; PSS contacts including home help, meals on wheels, and day centre visits; and any other prescribed medications. The volume of resource use for each cost component will be measured directly in the trial from patient records and using patient diaries. Patient records will be used to assess volume of secondary care use throughout the follow-up period. Patient diaries will be used to assess the volume of resource use for all types of contact during the first two years only. We will compare the secondary care volumes from the patient records in the first year to the secondary care volumes in the patient diaries to assess the accuracy of the patient diaries. Data on the volume of secondary care use will be taken from the patient records. Data on the volume of secondary care and PSS use will be taken from the patient diaries. Unit costs will be taken from standard published sources.

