The cost-effectiveness measures in the within-trial model will be the incremental cost per change in fatal or non-fatal stroke in any arterial territory during trial follow-up (the primary outcome in the main trial), as well as the incremental cost per quality-adjusted life year (QALY) gained. QALYs will be calculated based on the health related quality of life (HRQL) and mortality data collected during the trial. HRQL will be measured according to the EQ-5D (www.euroqol.org), which we will collect at each follow-up point for each individual patient at each follow-up point. Given the perspective of the evaluation, EQ-5D scores will be converted into utilities using an EQ-5D social tariff computed using data from a representative sample of the UK population (16). Patient-specific utility profiles will be constructed assuming a straight line relation between each of the patients EQ-5D scores at each follow-up point. The QALYs experienced by each patient from baseline to final follow-up years will be calculated as the area underneath this profile.

Multiple imputations by chained equations will be used to deal with missing EQ-5D and resource use values. Subsequent analyses of imputed data will include variance correction factors to account for additional variability introduced into parameter values as a result of the imputation process.

Cost-effectiveness will be calculated as the mean cost difference between vertebral angioplasty and stenting versus best medical treatment divided by the mean difference in outcomes (fatal or non-fatal stroke in any arterial territory /QALYs) to give the incremental cost-effectiveness ratio (ICER).

Non-parametric methods for calculating confidence intervals around the ICER based on bootstrapped estimates of the mean cost and QALY differences will be used (17) The bootstrap replications will also be used to construct a cost-effectiveness acceptability curve, which will show the probability that the new procedures are cost-effective for different values of the NHS' willingness to pay for an additional QALY. We will also subject the results to extensive deterministic (one-, two- and multi-way) sensitivity analysis. We will undertake cost-effectiveness analyses by patient sub-groups using pre-defined groups.

In the lifetime model cost-effectiveness will be calculated in terms of the incremental cost per QALY gained of the new procedures versus best medical care.

ETHICS

Ethics Committee

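### Within-trial cost-effectiveness: non-hospital costs stop at year 2, while hospital costs, strokes and QALYs run to the end of follow-up

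*Protocol*

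**What the plan says.** Four elements of the Protocol matter here.

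- **Non-hospital resource use.** The Economic Analysis section says: "Patient diaries will be used to assess the volume of resource use for all types of contact during the first two years only". The Patient Assessment Schedule gives the same window for UK patients: "health and social care contacts during the first two years will be collected prospectively using patient diaries".
- **Hospital resource use.** "Patient records will be used to assess volume of secondary care use throughout the follow-up period".
- **Effects.** One within-trial measure is "the incremental cost per change in fatal or non-fatal stroke in any arterial territory during trial follow-up". The other is cost per QALY: "The QALYs experienced by each patient from baseline to final follow-up years will be calculated as the area underneath this profile".
- **Length of follow-up.** "Follow-up will range from 2 years for the last recruited patients to up to about 8 years for first patients recruited".

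The ratio is defined as the mean cost difference over the mean outcome difference. No shorter window is set for either part. The list of costed components includes primary care, PSS, therapy after discharge and other prescribed medication.

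On sources, one sentence assigns secondary care to patient records, and the next says: "Data on the volume of secondary care and PSS use will be taken from the patient diaries". Neither names primary care. On EQ-5D, the Patient Assessment Schedule says that it "will be administered at each follow-up".

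**The concern.** A cost-effectiveness ratio needs its numerator and denominator to cover the same period. Here part of the numerator ends at month 24, while the rest of it and the whole denominator continue. A stroke in year 4 would count as an outcome, reduce QALYs and generate hospital costs, but any home help or primary care that followed would cost nothing. The same holds for care after year 2 that results from a stroke in year 1.

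The NHS and PSS perspective is then only partly delivered beyond year 2. NHS and PSS costs, QALYs and within-trial cost-effectiveness are all listed as secondary end points. This is not a detail awaiting an analysis plan, because the protocol itself fixes both windows.

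**Working it through.** The protocol states no figure for the overlap of the windows, so there is none to reproduce. The first step sets the windows side by side.

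| Quantity in the ratio | Source | Period |
|---|---|---|
| Hospital care | Patient records | All follow-up |
| Primary care, PSS, and therapy or medication not in hospital records | Diaries | Years 1–2 |
| Strokes | Trial follow-up | All follow-up |
| QALYs | EQ-5D and mortality | Baseline to last follow-up |

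Only the second row stops early.

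**Coverage per patient.** For a patient followed for T years (T at least 2), diary coverage is 2/T.

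| T (years) | Covered, 2/T | Uncovered, 1 − 2/T |
|---|---|---|
| 2 | 100% | 0% |
| 3 | 67% | 33% |
| 5 | 40% | 60% |
| 8 | 25% | 75% |

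**Average coverage.** The distribution of follow-up is not given. Assume that it is uniform over 2 to 8 years:

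- Without deaths, mean follow-up is (2 + 8)/2 = 5 years, and coverage of person-time is 2/5 = 40%.
- With deaths, the protocol expects over 80% alive at 5 years. Taking exactly 80% and a constant hazard, λ = −ln(0.8)/5 = 0.0446 per year. Mean person-years in the first two years are (1 − e^(−2λ))/λ = 1.91. The mean of (1 − e^(−λT))/λ over T from 2 to 8 is 4.43. Coverage is 1.91/4.43 = 43%.

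So 57–60% of person-time has no diary data under these assumptions.

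**Share of first strokes after year 2.** Person-time is not the same as events. The protocol's annual medical-arm risks are 12%, 6% and 4% in years 1 to 3.

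- Over three years, adding the annual figures, 4 of 22 points (18%) fall after year 2.
- If 4% a year is assumed to continue to year 5, 12 of 30 points (40%) do.
- Compounding the annual risks, with 4% a year continuing and uniform follow-up, the risk is 1 − 0.88 × 0.94 = 17.28% by year 2 and 26.63% by end of follow-up. The share after year 2 is 1 − 17.28/26.63 = 35%.

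**Whether imputation repairs it.** The protocol plans chained-equations imputation for missing resource use. That method learns from patients in whom the item was observed. After month 24 diary items are observed in nobody, so any values would rest on an extrapolation that the protocol does not describe.

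**Sources and EQ-5D.** Read together, the two source sentences give secondary care two sources and leave primary care unnamed. Separately, the QALY profile starts at baseline, but EQ-5D is scheduled only at follow-ups. The first follow-up common to both arms is at one month, so the profile has no stated starting value.

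**The case against.** Several stronger conclusions might be inferred, and the protocol does not support them.

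- **That all costs stop at two years.** They do not. Records supply secondary care throughout, so admissions for late strokes are costed. The gap is confined to non-hospital items.
- **That hospital care is counted twice.** Nothing says that record and diary volumes are added. The section plans to compare them for the first year as a check on the diaries. The second mention of secondary care is probably a slip for primary care, though that is an inference.
- **That primary care has no source.** The diaries cover every type of contact in years 1–2. Primary care is missing only from the closing pair of sentences, and from any stated source after year 2.
- **That the omission must be large because stroke care is mostly long-term social care.** The protocol gives no figures on this.

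Two further objections have some force. Therapy after discharge is not individually assigned to a source, and hospital-based therapy may be in the records; only the part outside them is affected. Also, the stroke measure was deliberately tied to the trial's primary outcome over all follow-up, and a 24-month horizon breaks that link. A stated extrapolation would be another way to align the windows.

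It could also be said that each component is to be measured from records as well as diaries, so records might fill the later years. But where the protocol says what the records supply, it is hospital or secondary care only. How unequal follow-up is handled, and whether QALYs are adjusted for baseline utility, can be left to an analysis plan. The mismatch itself survives these points.

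**Conclusion.** The point holds for non-hospital costs. As written, the within-trial ratio omits them after year 2 while counting hospital costs, strokes and QALYs to the end of follow-up. Per-patient diary coverage ranges from 100% to 25%, which needs no assumption beyond the stated 2 to about 8 years. The average of 40–43% of person-time rests on uniform follow-up and, for the upper figure, on 20% mortality at 5 years.

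These figures measure time without data. They do not measure missing money, and the effect on the ratio cannot be sized from the protocol. Its direction depends on the results: if stenting prevents strokes as the sponsor assumes (45% reduction), and strokes lead to community care, later savings would be left out and the ratio would lean against stenting.

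The source sentences are a probable wording slip, and the baseline EQ-5D is an ambiguity. Both need correcting, but neither shows double counting or a missing cost category in years 1–2. The point touches secondary economic end points in UK patients and leaves the primary clinical comparison unaffected.

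**What to change.** 1. Make the main within-trial ratio use a common 24-month horizon for all costs, strokes and QALYs. Planned minimum follow-up, the diaries and the year-2 telephone call with EQ-5D already support this.
2. Report the full-follow-up ratio as a secondary analysis only, with an explicit, stated extrapolation of non-hospital costs beyond month 24. Let later data also feed the lifetime model.
3. Name one source for each cost component. If the second source sentence was meant to read primary care and PSS, correct it; keep the comparison of records with diaries as a validation step.
4. State that EQ-5D is recorded at the baseline visit.

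The cost is protocol and health-economics wording, plus at most one questionnaire at an existing visit; patients already enrolled may lack a baseline value. The real downside is that strokes and QALYs after month 24 leave the main within-trial ratio, which then no longer matches the full-follow-up primary outcome. Under the continuing 4% assumption above, about 35% of first strokes in the medical arm would move to the secondary analysis and the lifetime model.

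### The EQ-5D is not scheduled at the baseline visit although QALYs are to run from baseline, so the utility profile has no start value and baseline utility is unavailable as a covariate

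*Protocol*

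**What the plan says.** Two places in the protocol set the timing of the EQ-5D. The Patient Assessment Schedule says that it "will be administered at each follow-up". The Economic Analysis section describes it as a measure "which we will collect at each follow-up point for each individual patient at each follow-up point".

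The visit list in the Patient Assessment Schedule gives "Hospital Visit 1 Baseline Visit" as a separate item. The first scheduled contact after it that both arms share is "Hospital Visit 3 at One Month post randomisation". On the content of hospital visits the protocol says: "At each hospital visit neurological assessment and recording of TIA, stroke and other complications will be performed". It adds a cardiovascular risk factor assessment. The EQ-5D is not in that list.

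The Economic Analysis section then builds the QALY in two steps: "Patient-specific utility profiles will be constructed assuming a straight line relation between each of the patients EQ-5D scores at each follow-up point", and "The QALYs experienced by each patient from baseline to final follow-up years will be calculated as the area underneath this profile". The ICER is the mean cost difference "divided by the mean difference in outcomes", with bootstrapped mean differences for the interval and the acceptability curve. Missing EQ-5D values are to be handled by chained-equation imputation. Randomisation is stratified by the site of stenosis and by nothing else that is stated.

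**The concern.** The area is defined from a time at which no score is scheduled. A site that follows the protocol literally would not ask for the EQ-5D at Hospital Visit 1. The first segment of each patient's profile would then run from nowhere to the one-month score. That score normally comes after the procedure in the stented arm, since stenting is due within two weeks of randomisation.

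The gap lies in data collection, so an analysis plan cannot close it. A plan can choose covariates, but not one that was never recorded. If no patient has a baseline score, the planned imputation has no observed baseline values to learn from.

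What is at stake is the QALY difference and the cost per QALY, both named secondary end points. Utility at entry usually predicts later utility. Without it, a chance difference between the arms at entry stays in the QALY difference and cannot be adjusted out.

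**Working it through.** The protocol gives no QALY figure to reproduce, and no utility SD, correlation or UK sample size. The inputs marked as assumed are therefore shown as ranges.

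**Inputs**
- First follow-up common to both arms: 1 month, i.e. 1/12 year (Patient Assessment Schedule).
- Horizon T: 2 years, the minimum planned follow-up. 3 years is also shown, the period used in the sample size section.
- UK patients per arm, n: assumed 100 to 200. The total target is 540, or 270 per arm, and the protocol expects the UK to recruit most patients.
- Utility SD: assumed 0.20 to 0.30.
- Slope b of follow-up utility on baseline utility: assumed 0.3 to 0.7.

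**Step 1. Weight of the baseline score in the area.** With straight lines between points, baseline counts for half the first interval: (1/12)/2 = 1/24 = 0.0417 year. That is 2.1% of a two-year span and 1.4% of a three-year span.

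**Step 2. Size of a one-standard-error chance imbalance at baseline.** SE = SD × √(2/n).
- Low: 0.20 × √(2/200) = 0.020.
- High: 0.30 × √(2/100) = 0.042.

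**Step 3. Direct effect through the first segment only.** SE × 1/24.
- Low: 0.020/24 = 0.0008 QALY.
- High: 0.0424/24 = 0.0018 QALY.

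If the first month were simply dropped, each patient would lose 0.6/12 = 0.05 to 0.8/12 = 0.07 QALY (assumed utility 0.6 to 0.8), largely equal in the two arms.

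**Step 4. Carry-over into the whole QALY difference without adjustment.** SE × [1/24 + b × (T − 1/24)].

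| Case | SE | b | T = 2 years | T = 3 years |
|---|---|---|---|---|
| Low | 0.020 | 0.3 | 0.020 × (0.0417 + 0.3 × 1.958) = 0.013 | 0.019 |
| High | 0.0424 | 0.7 | 0.0424 × (0.0417 + 0.7 × 1.958) = 0.060 | 0.090 |

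At the ceiling of 270 UK patients per arm, with SD 0.20 and b = 0.3, the two-year figure is still 0.011.

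**Step 5. Precision gained by adjustment.** With correlation r between baseline utility and the QALY total, the variance falls by r² and the SE by 1 − √(1 − r²).
- r = 0.3: variance 9%, SE 1 − √0.91 = 5%.
- r = 0.5: variance 25%, SE 1 − √0.75 = 13%.
- r = 0.7: variance 49%, SE 1 − √0.51 = 29%.

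**The case against.** **Baseline may have been intended.** The text says when the EQ-5D is given and does not exclude baseline. An area that starts at baseline presupposes a score there, and the doubled phrase in the Economic Analysis section suggests loose drafting. A reader might infer a decision to omit baseline, and the documents do not support that. What stands is that no section asks sites for the score.

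**The protocol does not say unadjusted.** A reader might infer that QALYs are to be compared as raw means. The stated estimator is a mean difference, which a regression can also supply, and covariates may be left to the analysis plan. This objection is right about the method. It does not help with the covariate, which has to be collected first.

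**Chance imbalance is not bias.** A reader might infer a biased ICER. Under randomisation the imbalance is sampling noise, and the planned bootstrap interval and acceptability curve already reflect it. This stands in full.

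**The first month can still be valued.** A reader might infer that procedural harm is lost. A pre-randomisation score measures no procedural harm, the one-month score captures harm that persists, and the baseline score carries only 1/24 year. This also stands.

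**A comparison with the expected benefit would mislead.** With SD 0.25, 245 per arm and slope 0.5, a 95% extreme over three years is 1.96 × 0.25 × √(2/245) × 0.5 × 3 = 0.066 QALY. It is tempting to set this against an expected gain of about 0.045 (10 points fewer strokes × an assumed 0.3 utility loss × 1.5 years). That puts an extreme beside a point estimate built on single guesses, and the one-SE figure on the same inputs is 0.034. The comparison should not be used.

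**Conclusion.** The inconsistency is real: the QALY area starts at a time for which no EQ-5D score is scheduled. It affects a secondary, UK-only outcome and leaves the primary end point and the sample size untouched.

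The absent start value matters little to the difference between arms. The absent covariate matters more, because a one-standard-error imbalance at entry would put roughly 0.013 to 0.060 QALY of avoidable noise into the two-year difference. Those figures rest wholly on the assumed SD, slope and UK numbers. The reduction of about 25% in variance rests on an assumed correlation of 0.5.

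The case for acting is that the loss cannot be recovered later and the remedy is cheap. The documents do not support a claim of systematic bias or of an analysis fixed as unadjusted.

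**What to change.** Amend the Patient Assessment Schedule and the Economic Analysis section together:

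- Administer the EQ-5D at Hospital Visit 1, before randomisation, and name every contact at which it is repeated. The schedule also mentions a post-procedure follow-up. If that counted as a follow-up point, the stented arm would have a score that the medical arm lacks, so the text should say whether it does.
- Start the utility profile at the baseline score.
- Estimate the mean QALY difference by regression on arm, baseline utility and the stenosis-site stratum, refitted within each bootstrap replicate.
- For patients already enrolled without a baseline score, include baseline utility in the planned chained-equation imputation, informed by the observed scores of later recruits.

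The cost is one short questionnaire at an existing visit and a few lines of text. The limitation is reliance on imputation for earlier recruits, which assumes that baseline and later utility are related in the same way in early and late recruits and recovers only part of the precision.

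### The within-trial ICER has no single time horizon: QALYs, strokes and hospital costs run to each patient's own last follow-up (2 to about 8 years), so it depends on the recruitment pattern and the QALY difference carries avoidable noise

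*Protocol*

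**What the plan says.** Four statements in the protocol combine.

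- **Length of follow-up** (Patient Assessment Schedule): "Follow-up will range from 2 years for the last recruited patients to up to about 8 years for first patients recruited". The last item of the schedule is "Telephone Follow-up Call Yearly from year 2 onward until study end", so follow-up ends at a calendar date and not at a fixed time from randomisation.
- **QALYs** (Economic Analysis): "The QALYs experienced by each patient from baseline to final follow-up years will be calculated as the area underneath this profile".
- **Strokes and hospital costs** (Economic Analysis): the clinical ratio is the "incremental cost per change in fatal or non-fatal stroke in any arterial territory during trial follow-up". For hospital costs, "Patient records will be used to assess volume of secondary care use throughout the follow-up period".
- **Estimator** (Economic Analysis): "Cost-effectiveness will be calculated as the mean cost difference between vertebral angioplasty and stenting versus best medical treatment divided by the mean difference in outcomes". Bootstrap intervals and an acceptability curve follow from the same differences.

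The section names no within-trial horizon, no censoring-adjusted estimator and no adjustment for length of follow-up. Multiple imputation is planned for missing EQ-5D and resource-use values, but the protocol does not say that it extends to years after study end. A separate lifetime model is planned.

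**The concern.** A patient recruited first can be observed for about four times as long as one recruited last (8 years against 2), and accumulates QALYs and hospital costs accordingly, for a reason unrelated to treatment. There are two consequences.

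1. **Undefined horizon.** The stenting procedure is paid for at the start, while the QALY benefit of avoided strokes grows with time. A mean over patients followed for 2 to 8 years answers neither a 2-year nor an 8-year question. Two trials with the same treatment effects but different recruitment curves would expect different costs per QALY and different acceptability curves.
2. **Avoidable noise.** Planned follow-up length is fixed by the randomisation date and strongly predicts a patient's QALY total. If it is ignored, its variation stays in the standard error of the QALY difference.

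The within-trial ratio is a listed secondary end point, and the planned acceptability curve is read against NHS willingness to pay.

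**Working it through.** The documents give no QALY, utility or ICER figure, so there is none to reproduce.

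**Inputs from the protocol**
- Control stroke risk 12%, 6% and 4% in years 1 to 3, and hazard ratio 0.55 (Sample Size Calculations). I use the yearly risks as printed.
- More than 80% alive at 5 years (Economic Analysis), taken as 80%: λ = −ln(0.80)/5 = 0.0446 a year.
- Follow-up from 2 to 8 years (Patient Assessment Schedule).

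**Assumptions, not in the documents**
- Stroke risk 4% a year after year 3.
- Utility loss of 0.25 after a stroke.
- Baseline utility mean 0.70, SD 0.15 to 0.30 (mean 0.60 as a variation).
- Planned follow-up F spread over 2 to 8 years: even (mean 5), front-loaded with linearly rising density (mean 6), or back-loaded with linearly falling density (mean 4).

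**Step 1: gain at a fixed horizon.** With control stroke-free probability S(t), the difference in the probability of having had a stroke is d(t) = S(t)^0.55 − S(t).
- 2 years: S = 0.88 × 0.94 = 0.8272, so d = 0.9009 − 0.8272 = 0.074.
- 8 years: S = 0.8272 × 0.96^6 = 0.6475, so d = 0.7874 − 0.6475 = 0.140.

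The QALY gain to horizon H is G(H) = 0.25 × ∫₀ᴴ e^(−λt) d(t) dt. This gives 0.021 at 2 years, 0.081 at 5 and about 0.151 at 8.

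**Step 2: what the stated estimator targets.** The difference in mean totals has expectation E[G(F)] over the recruitment curve. The stroke column is ∫ e^(−λt) h [e^(−H) − 0.55 e^(−0.55H)] dt, with h the control stroke hazard and H here its cumulative value, averaged in the same way.

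| Recruitment | QALY gain | Stroke difference, points |
|---|---|---|
| Back-loaded | 0.061 | 9.2 |
| Even | 0.082 | 10.1 |
| Front-loaded | 0.104 | 11.0 |

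The QALY gain varies by 0.104/0.061 = 1.7. Strokes vary less (10.1/9.2 = 1.10 between even and back-loaded) because most risk falls early.

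One costed illustration assumes a procedure cost of 5,000, a stroke cost of 10,000 and a utility loss of 0.20. The cost per QALY is about 45,000 front-loaded, 59,000 even and 83,000 back-loaded, a ratio of 83/45 = 1.8.

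**Step 3: noise.** Let L = min(time to death, F) and Q = utility × L, with utility mean μ and SD σ. Then
- E[L|F] = (1 − e^(−λF))/λ;
- share explained by F = μ² Var(E[L|F]) / {(μ² + σ²)E[L²] − μ²E[L]²}.

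For even recruitment with μ = 0.70 and σ = 0.20: Var(E[L|F]) = 1.929, E[L²] = 23.44 and E[L] = 4.428. The share is 0.49 × 1.929 / (0.53 × 23.44 − 0.49 × 19.61) = 0.945/2.82 = 34%.

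The extremes are 43% (μ = 0.70, σ = 0.15, back-loaded) and 10% (μ = 0.60, σ = 0.30, front-loaded). Adjustment multiplies the standard error by √(1 − share), a reduction of 1 − √0.90 = 5% to 1 − √0.57 = 25%.

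Simulation with strokes included, 400 UK patients (assumed) and utility SD 0.20 gave:

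| Recruitment | SE unadjusted | SE adjusted |
|---|---|---|
| Even | 0.160 | 0.134 |
| Back-loaded | 0.129 | 0.105 |
| Front-loaded | 0.172 | 0.157 |

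Planned follow-up explained under 1% of the variance of the stroke outcome. The variance of costs was not computed.

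**Step 4: what adjustment does not do.** Regressing simulated QALY totals on arm and planned follow-up gave 0.082 (even) and 0.061 (back-loaded), against 0.083 and 0.060 unadjusted. The dependence on recruitment is unchanged.

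**The case against.** **Estimator detail belongs in an analysis plan that is not shown.** This stands in part. The protocol says "divided by the mean difference in outcomes" without saying unadjusted, so a reader who infers that crude means are mandated goes beyond the text. But the protocol does fix the QALY total as running to each patient's final follow-up, with follow-up ending at study end. An analysis plan could set a common horizon only by departing from that definition.

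**The arms remain comparable.** This stands in full. A reader might infer a biased comparison. Randomisation gives both arms the same expected distribution of follow-up, so there is no bias between arms.

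**The lifetime model supplies a horizon free of recruitment, and sensitivity analyses are planned.** This stands in part. The within-trial ratio is a separate secondary end point, and cost per stroke is planned only within the trial. Nothing says that the sensitivity analyses vary the horizon.

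**The stroke outcome deliberately matches the primary end point.** True, and for strokes the effect is small. A reader might extend the precision argument to cost per stroke, but planned follow-up explains almost none of the stroke variance.

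**The precision gain rests on assumptions.** This stands. It is tempting to say that about a third of QALY variance is avoidable. That holds for even or back-loaded recruitment with a utility SD near 0.20. The documents give neither the SD nor the recruitment shape.

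**Conclusion.** The point holds as one of definition and precision, for a secondary, UK-only economic end point. Followed as written, the within-trial ICER is a recruitment-weighted mixture of horizons from 2 to about 8 years. With identical treatment effects the expected QALY gain runs from about 0.06 (back-loaded) to 0.10 (front-loaded). Separately, variation in recruitment date is left as noise in the QALY difference: about 10% to 43% of QALY variance, worth roughly 5% to 25% of its standard error.

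These sizes depend on the assumed utilities, stroke decrement, later stroke risk and recruitment shapes. The mixed horizon does not: it follows from the protocol's own definitions.

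A reader might also infer that adjusting for planned follow-up cures both faults. It does not, because the adjusted difference is still averaged over the recruitment curve.

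**What to change.** 1. **State one within-trial horizon.** Estimate costs, strokes and QALYs to it by summing yearly means among patients whose planned follow-up covers that year, or use another censoring-adjusted estimator. This step removes the dependence on recruitment.
2. **If totals over all follow-up are also reported,** estimate the QALY difference by regression on arm, with planned follow-up length (randomisation date to study end) and stenosis site as covariates, within each imputed and bootstrap data set. Describe this as a gain in precision only.

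**Cost.** Only analysis wording changes. The randomisation date is known and stenosis site is already the stratification factor, so no new data are needed.

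The choice of horizon has a price. At 2 years every patient's planned follow-up is complete, but the expected QALY gain is only about 0.021 on the assumptions above. Beyond 2 years, the year-by-year estimate is less precise if recruitment is back-loaded: a standard error of 0.151 in the simulation, against 0.129 for the unadjusted total, though the two estimate different quantities. A longer horizon also needs a statement on community-care costs, because "Patient diaries will be used to assess the volume of resource use for all types of contact during the first two years only".
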